10.3. STATISTICAL PARAMETERS AND STATISTICAL ANALYSIS PLAN

Safety analysis will be conducted in the safety analysis set. Safety evaluation will include all patients who receive at least one dose of study drug. The safety analysis is based on the abnormality of laboratory test and clinical adverse events. Considering the percentage of laboratory abnormalities or clinical adverse events, descriptive statistics (or Fisher's exact test, Chi-square test for comparison between parameters) will be used. The primary endpoint, the objective response rates, will be described with percentage (%) and 95% confidence intervals. The survival outcomes, secondary endpoints, will be calculated using Kaplan-Meier method, compared using long-rank test and described with 95% confidence intervals. The disease-control rates will be described with percentage (%) and 95% confidence intervals, and compared using odds ratio and Chi-square tests. The Kaplan-Meier method will be used to estimate progression-free and overall survival curves, and the Cox proportional hazards regression model will be used for multivariate analysis of prognostic factors for survival outcomes.

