6. STUDY POPULATION

6.1. ELIGIBILITY

6.1.1. INCLUSION CRITERIA

1. Histologically or cytologically confirmed adenocarcinoma of the colon or the rectum.
2. Mismatch repair deficient or microsatellite instable (defined below), or *POLE* mutated tumors
 - A. Mismatch repair deficient: loss of expression by immunohistochemical stains ≥ 1 out of 4 markers (MLH1, MSH2, MSH6, PMS2)
 - B. Microsatellite instable: loss of stability ≥ 2 out of 5 gene panels (BAT-25, BAT-26, D2S123, D5S346, D17S250)
 - C. *POLE* gene: P286R mutation or other mutation

3. Refractory to prior fluoropyrimidines, irinotecan and oxaliplatin (progressed during or within 6 months of those agents).
4. ≥ 1 measurable lesion(s) by RECIST 1.1.
5. Unresectable advanced or metastatic disease.
6. Age over 20 years old.
7. ECOG performance status of 0-1 or lower.
8. Adequate organ functions.
 - A. Bone marrow function: Hemoglobin ≥ 9.0 g/dL, ANC $\geq 1,500/\text{mm}^3$, platelet $\geq 100,000/\text{mm}^3$
 - B. Hepatic functions: bilirubin ≤ 1.5 X ULN, AST/ALT ≤ 2.5 X ULN (≤ 5 X ULN in cases of liver metastasis)
 - C. Renal functions: serum Cr ≤ 1.5 X ULN or calculated CCr (Cockcroft) > 40 ml/min
9. Be willing and able to comply with the protocol for the duration of the study.
10. Give written informed consent prior to study-specific screening procedures, with the understanding that the patient has the right to withdraw the study at any time, without prejudice.
11. Female subjects must either be of non-reproductive potential (≥ 60 years old and no menses for ≥ 1 year without an alternative medical cause, or history of hysterectomy, or history of bilateral tubal ligation, or history of bilateral oophorectomy) or must have a negative serum pregnancy test upon study entry.
12. Women of childbearing potential and men must agree to use adequate contraception since signing of the IC form until at least 90days after the last study drug administration.

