6.1.2. EXCLUSION CRITERIA

All of the following exclusion criteria should be checked at the time of screening procedure.

1. Any prior treatment with PD-1 or PD-L1 inhibitor, including durvalumab.
2. Involvement in the planning and/or conduct of the study.
3. Receipt of the last dose of chemotherapy ≤ 28 days prior to the first dose of study drugs.
4. Mean QT interval corrected for heart rate (QTc) ≥ 470 msec calculated from 3 electrocardiograms (ECGs) using Frediricia's Correction.
5. Any unresolved toxicity NCI CTCAE Grade ≥ 2 from previous anticancer therapy with the exception of alopecia, vitiligo, and the laboratory values defined in the inclusion criteria
6. Patients with Grade ≥ 2 neuropathy will be evaluated on a case-by-case basis after consultation with the Study Physician.

7. Patients with irreversible toxicity not reasonably expected to be exacerbated by treatment with durvalumab may be included only after consultation with the Study Physician.
8. Any concurrent chemotherapy, IP, biologic, or hormonal therapy for cancer treatment. Concurrent use of hormonal therapy for non-cancer-related conditions (eg, hormone replacement therapy) is acceptable.
9. Current or prior use of immunosuppressive medication within 14 days before the first dose of durvalumab, with the exceptions of intranasal and inhaled corticosteroids or systemic corticosteroids at physiologic doses, which are not to exceed 10 mg/day of prednisolone, or an equivalent corticosteroid.
10. Concurrent or previous history of another primary cancer within 3 years prior to randomisation except for curatively treated cervical cancer in situ, non-melanomatous skin cancer, superficial bladder cancer (pTis and pT1) and curatively treated thyroid cancer of any stage. Concurrent, histologically confirmed, unresected thyroid cancer without distant metastasis could be allowed with the agreement of the chief principal investigator.
11. Uncontrolled CNS metastases; permitted if asymptomatic or neurologically stable.
12. Prior radiation therapy would be permitted, but non-irradiated evaluable lesions should be present at study entry.
13. Radiation therapy during study treatment is not permitted, but if the local investigator decides that radiation therapy should be given during study treatments, he should be convinced that there is no evidence of disease progression with agreement of the chief principal investigator.
14. Congestive heart failure \geq New York Heart Association (NYHA) class 2.

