9. ADVERSE EVENTS

9.1. DEFINITIONS

9.1.1. ADVERSE EVENT

The term **adverse event** covers any unfavorable and unintended sign, symptom, syndrome,

or illness that develops or worsens during the period of observation in the clinical study. Clinically relevant abnormal results of diagnostic procedures including abnormal laboratory findings (e.g., requiring unscheduled diagnostic procedures or treatment measures, or resulting in withdrawal from the study) are considered to be adverse events.

Worsening of a sign or symptom of the condition under treatment will normally be measured by safety parameters. However, if the outcome fulfills the definition of «serious adverse event», it must be recorded as such.

The adverse event may be:

- A new illness
- Worsening of a concomitant illness
- An effect of the study medication, including comparator
- A combination of two or more of these factors
- No causal relationship with the study medication or with the clinical study itself is implied by the use of the term «adverse event».
- Adverse events fall into the categories «non serious» and «serious».

Surgical procedures themselves are not adverse events; they are therapeutic measures for conditions that require surgery. The condition for which the surgery is required is an adverse event, if it occurs or is detected during the study period. Planned surgical measures permitted by the clinical study protocol and the condition(s) leading to these measures are not adverse events, if the condition(s) was (were) known before the start of study treatment. In the latter case the condition should be reported as medical history.

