
THIS shaded area is guidance only for management of “Hepatitis (elevated LFTs)” in HCC patients (or secondary tumour involvement of the liver with abnormal baseline values [BLV])
			
 - For hepatitis C (HCV) + patients: evaluate quantitative HCV viral load. - Consider consulting Hepatology or Infectious Diseases specialists regarding changing or starting antiviral HBV medications if HBV viral load is >2000 IU/ml. - Consider consulting Hepatology or Infectious Diseases specialists regarding changing or starting antiviral HCV medications if HCV viral load has increased by ≥ 2-fold. - For HCV+ with Hepatitis B core antibody (HBcAb)+: Evaluate for both HBV and HCV as above.

See instructions at bottom of shaded area if transaminase rise is not isolated but (at any time) occurs in setting of either increasing bilirubin or signs of DILI/liver decompensation
	
Isolated AST or ALT >ULN and $\leq 2.5 \times$ BLV,
	
 - No dose modifications. - If ALT/AST elevations represents significant worsening based on investigator assessment, then treat as described for elevations in the row below. - For all transaminase elevations, see instructions at bottom of shaded area if transaminase rise is not isolated but (at any time) occurs in setting of either increasing bilirubin or signs of DILI/liver decompensation 	
	
ALT or AST > 2.5-$\leq 5 \times$ BLV and $\leq 20 \times$ULN
	
 • Hold study drug/study regimen dose until resolution to AST or ALT $\leq 2.5 \times$BLV . • If toxicity worsens, then treat as described for elevations in the rows below. If toxicity improves to AST 	
 - Regular and frequent checking of Transaminases and total bilirubin (e.g., every 1 to 3 days) until elevations of these are improving or resolved. - Recommend consult hepatologist; consider abdominal ultrasound, including Doppler assessment of liver perfusion. - Consider, as necessary, discussing with Clinical Study Lead.

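### Section 10.3 summarises laboratory safety as a percentage of abnormalities with no baseline reference, although abnormal values are allowed at entry

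*Combined protocol and SAP*

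**What the plan says.** Section 10.3 gives safety two components: "The safety analysis is based on the abnormality of laboratory test and clinical adverse events". Both are then summarised in one sentence: "Considering the percentage of laboratory abnormalities or clinical adverse events, descriptive statistics (or Fisher's exact test, Chi-square test for comparison between parameters) will be used". Sections 10.1 to 10.4 do not define an abnormality. They give no threshold, grade or time window, and mention no baseline comparison, shift table or treatment-emergent rule.

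Eligibility (section 6.1.1, criterion 8) allows some abnormal values at entry. For liver tests the limits are bilirubin at 1.5 x ULN and "AST/ALT ≤ 2.5 X ULN (≤ 5 X ULN in cases of liver metastasis"). Haemoglobin may be as low as 9.0 g/dL. Serum creatinine may exceed 1.5 x ULN if calculated clearance is above 40 mL/min, because the two renal conditions are alternatives. Section 6.1.2, criterion 5, excludes unresolved Grade 2 or higher toxicity from earlier anticancer treatment, "with the exception of alopecia, vitiligo, and the laboratory values defined in the inclusion criteria".

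The adverse event component does have a baseline reference. Section 9.1.1 covers a sign, symptom, syndrome, "or illness that develops or worsens during the period of observation in the clinical study", and it brings in "Clinically relevant abnormal results of diagnostic procedures including abnormal laboratory findings". Section 9.1.4 records grade changes and the maximum grade for each event.

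**The concern.** Safety is a secondary objective (section 4.2). Several of the adverse events of special interest in section 9.1.3 are wholly or partly laboratory findings: transaminases, creatinine, amylase and lipase, and thyroid function. A reader of the final report will look at the laboratory table for these.

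If that table gives the percentage of patients with an abnormal value on treatment, it can go wrong in two directions. A patient who entered with raised transaminases and stayed there adds to the percentage, although nothing happened on durvalumab. A patient who entered at 2 x ULN and rose to 8 x ULN is abnormal before and after, so a yes/no count does not register the rise. With one arm, no comparison group shows how much of the percentage is background.

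There is also a reproducibility problem. One analyst could count every out-of-range value and another only worsened grades. Both would comply with section 10.3 and could report quite different rates from the same data.

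**Working it through.** **1. The plan's own figures.** The documents give no expected rate for any laboratory abnormality, so there is no laboratory figure to reproduce. The sample size is not in dispute. The two-stage rule in section 10.2 (2 or more responses in 10, then 6 or more in 29) has exact one-sided type I error 0.047 at a 10% response rate and power 0.805 at 30%. Allowing 10% dropout, 29/(1 − 0.10) = 32.2, rounded up to 33. Nothing below changes these.

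**2. Which components have a baseline reference.**

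| Component | Baseline reference in the documents |
|---|---|
| Adverse events, including clinically relevant laboratory findings | Yes: must be new or worse during observation (9.1.1); grade changes recorded (9.1.4) |
| Laboratory abnormality percentage (10.3) | None stated |

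Only the second row is exposed.

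**3. Can patients be abnormal at entry?** Yes, for AST/ALT, bilirubin, haemoglobin and creatinine, by criterion 8. Amylase, lipase and thyroid tests are not in criterion 8, so the exception in exclusion 5 does not cover them, and Grade 2 or higher residual treatment toxicity in those tests is excluded. Lower-grade abnormality, or abnormality from another cause, has no numerical limit there.

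**4. Illustration of sensitivity.** Let b be the share of treated patients abnormal at entry who remain abnormal, and t the new-onset rate among the rest. Both are assumptions; the documents give neither. The literal percentage is

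crude = b + (1 − b) × t

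For example, with b = 0.10 and t = 0.05: 0.10 + 0.90 × 0.05 = 0.145. Assuming all 33 patients are treated:

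| b | Patients (33 × b) | t = 5% | t = 10% | t = 20% |
|---|---|---|---|---|
| 10% | 3.3 | 14.5% | 19% | 28% |
| 20% | 6.6 | 24.0% | 28% | 36% |
| 30% | 9.9 | 33.5% | 37% | 44% |
| 50% | 16.5 | 52.5% | 55% | 60% |

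The ratio of crude rate to t runs from 2.9 to 10.5 at t = 5%, from 1.9 to 5.5 at t = 10%, and from 1.4 to 3.0 at t = 20%. The ratio therefore depends heavily on the chosen t. In absolute terms, b is the part of the crude rate that is pre-existing: three such patients contribute 3/33 = 9.1 percentage points.

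**5. Are the data there to do better?** Yes. Section 8.1 schedules blood count, chemistry, amylase and lipase at screening and every cycle, and thyroid tests at screening and every 8 weeks.

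**The case against.** The strongest reply is that the adverse event component already does the important work. The events of special interest are adverse events, section 9.1.1 restricts these to new or worsening findings, and section 9.1.4 collects grade changes. A clinically relevant rise in a patient already abnormal should therefore appear in the adverse event tables. This stands, and it confines the point to the separate laboratory-value summary. It does not remove the point: entry into the adverse event tables depends on a judgement of clinical relevance, and section 10.3 still lists laboratory abnormality as an output of its own.

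Three stronger readings are tempting, and the documents do not support them.

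- A reader might infer that the plan rules pre-existing abnormalities in. It does not; it is silent. The consequence is a risk of literal application, not a stated rule.
- A reader might infer that anyone may enter at 5 x ULN. That limit applies only with liver metastasis; otherwise it is 2.5 x ULN.
- A reader might see a contradiction with Appendix A, which scales transaminases to baseline in hepatocellular carcinoma ("or secondary tumour involvement of the liver with abnormal baseline values [BLV"]). Its general hepatitis rows use multiples of ULN, and the appendix guides toxicity management rather than analysis. Different scales for these two purposes do not conflict.

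It is also fair to say that screening values exist, so shift tables could be produced at reporting without being planned. That makes the repair easy, but it leaves the choice of measure until after the data are seen.

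**Conclusion.** The point holds in a limited form. As specified, the laboratory percentage has no baseline reference. Applied literally, it can include abnormality present at entry and cannot show worsening in patients already abnormal, with no control arm to reveal the background.

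The effect is confined to one descriptive secondary safety summary. The primary endpoint, the two-stage rule, the sample size and the adverse event tables are not affected, so it would be wrong to conclude that the trial's rates of immune-mediated harm are generally unreliable.

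The size of any distortion cannot be derived from the documents. The tabulated figures rest on an assumed entry share, an assumed new-onset rate and the assumption that every patient abnormal at entry stays abnormal. They show sensitivity and should not be quoted as an estimate. The change is worth making because it yields an interpretable measure at almost no cost.

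**What to change.** In section 10.3, replace the laboratory percentage with the percentage of treated patients whose worst on-treatment CTCAE grade (version 4.0, as in section 8.1) is higher than their screening grade. Add a table of screening grade by worst on-treatment grade for AST, ALT, bilirubin, creatinine, amylase, lipase and haemoglobin, and show how many patients have no on-treatment value.

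For TSH and free T4, tabulate screening category (low, normal, high) against worst on-treatment category, so that patients abnormal at screening are shown as well as those who become abnormal.

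Optionally, for patients with abnormal liver tests at screening, describe peak AST/ALT as a multiple of the baseline value. This is a descriptive addition and changes no management rule.

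The cost is a few sentences of analysis text and some extra tables from values already scheduled. No new test or visit is needed, and there is no material downside. The change and its reason should be recorded as section 11.5 requires.

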10.4. FINAL ANALYSIS

Final analysis will be conducted in all patients for all endpoints at completion of follow-up.

11. ETHICAL AND LEGAL ASPECTS

11.1. GOOD CLINICAL PRACTICE (GCP)

This study is to be conducted according to globally accepted standards of good clinical practice (as defined in the Korean GCP), in agreement with the Declaration of Helsinki and in keeping with local regulations.

11.2. DELEGATION OF INVESTIGATOR DUTIES

The investigator should ensure that all persons assisting with the study are adequately qualified, informed about the protocol, any amendments to the protocol, the study treatments, and their study-related duties and functions. The investigator should maintain a list of sub-investigators and other appropriately qualified persons to whom he or she has delegated significant trial-related duties.

11.3. SUBJECT INFORMATION AND INFORMED CONSENT

Before being enrolled in the clinical study, subjects must consent to participate after the nature, scope, and possible consequences of the clinical study have been explained in a form understandable to them. An informed consent document that includes both information about the study and the consent form will be prepared and given to the subject. This document will contain all the elements required by the KGCP and any additional elements required by local regulations. The document must be in a language understandable to the subject and must specify who informed the subject. Where required by local law, the person who informs the subject must be a physician. After reading the informed consent document, the subject must give consent in writing. The subject's consent must be confirmed at the time of consent by the personally dated signature of the subject and by the personally dated signature of the person conducting the informed consent discussions. If the subject is unable to read, oral presentation and explanation of the written informed consent form and information to be supplied to subjects must take place in the presence of an impartial witness. Consent must be confirmed at the time of consent orally and by the personally dated signature of the subject or by a local legally recognized alternative (e.g., the subject's thumbprint or mark). The witness and the person conducting the informed consent discussions must also sign and personally date. A copy of the signed consent document must be given to the subject. The original signed consent document will be retained by the investigator. The investigator will not undertake any measures specifically required only for the clinical study until valid consent has been obtained. The investigator should inform the subject's

primary physician about the subject's participation in the study if the subject has a primary physician and if the subject agrees to the primary physician being informed.

11.4. CONFIDENTIALITY

All the information related to this study will be used only for research and all personal data will be handled in strictest confidence. Only the subject number and subject initials will be recorded in the case report form, and all personal information and/data will be handled as independent data to enable records to be identified with securing confidentiality. Study findings stored on a computer will be stored in accordance with local data protection laws. The subjects will be informed that representatives of the sponsor, institutional review board (IRB), or regulatory authorities may inspect their medical records to verify the information collected, and that all personal information made available for inspection will be handled in strictest confidence and in accordance with the Korean Medical Service Act.

11.5. PROTOCOL AMENDMENTS

Without investigators agreement this clinical study protocol will not be modified. Once the study has started, amendments should be made only in exceptional cases. The changes then become part of the clinical study protocol. When contents of the analysis protocol are modified, the contents of all modifications will be described in the analysis protocol and final report of the study. Background for modification of the analysis protocol will be recorded.

11.6. APPROVAL OF THE CLINICAL STUDY PROTOCOLS AND AMMENDMENTS

Before the start of the study, the clinical study protocol, informed consent document, and any other appropriate documents will be submitted to the IRB with a cover letter or a form listing the documents submitted, their dates of issue, and the site (or region or area of jurisdiction, as applicable) for which approval is sought. If applicable, the documents will also be submitted to the authorities, in accordance with local legal requirements. Before the first subject is enrolled in the study, all ethical and legal requirements must be met. The IRB and, if applicable, the authorities must be informed of all subsequent protocol amendments and administrative changes, in accordance with local legal requirements. Amendments must be evaluated to determine whether formal approval must be sought and whether the informed consent document should also be revised. The investigator must keep a record of all communication with the IRB and, if applicable, between a coordinating investigator and the IRB. This also applies to any

communication between the investigator (or coordinating investigator, if applicable) and the authorities.

11.7. CLOSURE OF THE STUDY

The study must be closed at the site on completion. Furthermore, the sponsor or the investigator has the right to close this study site at any time. As far as possible, premature closure should occur after mutual consultation. Depending on local legislation, it may be necessary to inform IRB and the regulatory authorities when the study site is closed.

11.8. FINANCIAL DISCLOSURE

Not applicable to this study

12. Exploratory biomarker studies

Additional genetic tests will be performed in tumor tissues of patients participating in the study, and tests are performed to find predictive factors for treatment in patients with and without response. At least 10 slides from the paraffin block of the tumor tissue (primary or metastatic) will be prepared, therefore, in some patients with both primary and metastatic tumor tissues, a total of 20 (10) primary and metastatic sites can be prepared. The screening number and date of collection will be described and delivered to the Asan Medical Center, Seoul, Korea. The details of sample delivery, slide production, processing and delivery shall be as provided to each joint research institution. Providing slides for biomarker studies is not mandatory for participation in this study. However, because of the use of the stored tumor tissue, the patient is not burdened with any additional expense or procedure, and encourages active provision of the patient if there is no additional personal information or the risk of exposure of genetic information.

Biomarkers to be examined are as follows.

- Opal Multiplex Tissue Staining with Opal™ including PD-1 and PD-L1

